## **5.0 Number of Subjects**

Two nursing homes will be recruited for comparison of LSB with care as usual. A power analyses for a MANOVA, with 2 groups and 2 dependent variables, was conducted in G\*Power Version 3.1.9.2 [32] to determine a sufficient sample size. Using an alpha ( $\alpha$ ) of .05, and a large effect size of  $d = .94$  [33], a sample size of 20 could achieve a power of 95% to detect between group differences.

Prior research in long-term care facilities indicates that oversampling by 15-20 percent is an efficient way to deal with attrition. This study will recruit 24 residents, or 12 residents per NH, to ensure a sample size of 20. From these two NHs, a minimum of 20 NH residents (10 per NH) and a maximum of 24 NH residents (12 per NH) will be recruited.

**FULL PROTOCOL TITLE:** The Effectiveness of Life Story Book on Depression and Meaning in Life for Mentally Alert Residents of Nursing Homes

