### *Description of all research procedures being performed and when they are performed:*

After identifying potential participants, private informational meetings with the research team which will include the PI and two research assistants -will be conducted with each potential participant where initial screening, using the SIS, will be administered by the PI. (*Please see attached screening script/tool*). If the resident is eligible, and would like to participate, the research team will further explain the study, including the length of the study-10 weeks with six visits, length of the visits 1- hour, three weeks with no visits, and the measures that will be

**FULL PROTOCOL TITLE:** The Effectiveness of Life Story Book on Depression and Meaning in Life for Mentally Alert Residents of Nursing Homes

collected. Full disclosure and written consents will be explained with plenty of time for any questions or clarification before consent forms are signed. The consent form will include the purpose, procedures, risks and costs of participating in the LSB. Again, there will be no costs for participating in the study and the research team will receive no monetary income from the LSB. In addition, the LSB will be the property of the participant, along with any scanned photos or stories written. This will be signed by each participant, each RA, and the PI. A copy of the consent form will be given to each participant. Additional information will be provided for those participants who would like to request their family's cooperation to secure photos and/or memorabilia. (*See attached information sheet*).

Although the recruitment of participants is for mentally alert residents, if they have given durable power of attorney to others, it may be necessary, per their NH regulations, to obtain informed consent from their designated durable powers of attorney [35], [36], [37]. The durable power of attorney will be contacted, permission sought, and the consent form signed. The consent form will also include an agreement that the LSB ownership will be with the participant. [38] A copy of the consent form will be given to the durable power of attorney.

Participants will be notified for scheduling of the LSB intervention, by their preferred method of notification, once recruitment is completed. When participant recruitment levels are met, the research team will contact the participants to schedule their first visit. LSB visits for all participants will begin the same week.

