NH-B participants will be scheduled for post-tests in 4 weeks, which will include repeating an overview of the study, including the number of sessions and length of time for each session. A written postcard will be given to each participant with the date, time and contact information of their RA for their scheduled post-test. A follow-up postcard will be sent to the participant each week until week # 4, when a reminder phone call will also be made by their RA the day before their visit is scheduled. Until that time, the resident will continue to receive care as usual in their NH.

*Description of the Intervention:*

**Life Story Book.** LSB provides a person the opportunity to chronologically share their life experiences and memories [25]. The LSB will include a combination of written information, photographs of significant people, places or events, and personal narratives from the stages of life that the participant would like to include.

The duration of the intervention will be three-1-hour visits, not including the visits for the pretest and the post-tests measures collected, for a total of five visits. Each visit will begin with the RA assessing the environment and the participant's needs, making sure that the participant can hear and see the RA, and that the seating arrangement is comfortable before beginning. Assessing the environment will include: assessing for privacy, lighting, noise level, temperature and seating arrangement [39]. It will be important to monitor the participant's needs for any other difficulties assessed that may need to be tended to and adjustments or accommodations made. This is crucial to adequately accommodate the older adults' needs. Again, the RAs will remain flexible in regard to the length of time per visit for the sake of the older participants. For example, two 30-minute sessions may be used, as could rescheduling for health issues, or other creative ways to accommodate the needs of the participant as much as possible.

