**20.0 Provisions to Protect the Privacy Interests of Subjects**

Participants will be provided with some examples of the *Life Review and Experiencing Form* questions as part of the informed consent process; in addition to the purpose of the

study and the necessity of disclosing some personal information. This will be clearly explained as part of the consent process. Participants will be informed that only the research team will have access to the LSB intervention transcripts and survey instruments. Participants will also be informed that they can refuse to answer any question or withdraw from the study at any time, without penalty, and without giving a reason for withdrawing from the study.

All survey instruments will be administered by the PI, a licensed master social worker who has experience working with older adults in nursing homes. The LSB intervention will be conducted by two social work/medical professionals who will be provided training, by the PI, for working with older adults in nursing homes. In addition, participants can ask questions about their participation in the research process at any time.

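### Nothing defers photo and memorabilia gathering in NH-B until after post-test 1, so the only contrast of LSB with care as usual may be diluted

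*Combined protocol and SAP*

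**What the plan says.** The design (section 10.0, Study Design) is a switching replication in two homes. NH-A has LSB between the pre-test and post-test 1; NH-B has care as usual over that period and LSB afterwards. Hypotheses I and II (section 1.0) both compare LSB with care as usual, and section 25.0 tests them with a MANCOVA that uses pre-test scores as covariates.

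For NH-B's waiting period of four weeks, section 10.0 says: "Until that time, the resident will continue to receive care as usual in their NH".

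Four other statements bear on what happens before and at post-test 1:

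- In the account of the consent meeting, which is the same for both homes, section 10.0 says: "Additional information will be provided for those participants who would like to request their family's cooperation to secure photos and/or memorabilia".
- NH-B's post-test visit at week 4 is one "which will include repeating an overview of the study, including the number of sessions and length of time for each session".
- Section 21.0 has the consent form reviewed at the first visit and again at post-test 1, without limiting this to one home.
- Section 10.0 also says: "LSB visits for all participants will begin the same week".

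Sections 2.0 and 10.0 (Description of the Intervention) both count photographs among the contents of the book. Section 2.0 adds memorabilia, and section 10.0 describes scanning both into the book.

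**The concern.** At post-test 2 both homes have had LSB. Post-test 1 is therefore the only point at which LSB can be compared with residents who have not yet received it, and both hypotheses rest on it.

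The family sheet is not neutral paperwork, because it opens the way to one component of the intervention. In NH-A, gathering photographs after the pre-test is part of LSB. In NH-B, the same activity over the same weeks falls inside the comparator. Adjusting for the pre-test cannot remove an exposure that arises in the control home after the pre-test.

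Two further consequences follow from the stated timing. Visits begin only when recruitment is complete (sections 8.0 and 10.0), so a resident who consents early, in either home, may start gathering before the pre-test; any benefit is then in the baseline and lost from the measured gain. NH-B families also have about four more weeks to collect material than NH-A families, so the two deliveries of LSB are less alike than the design intends.

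Separately, an overview or consent review given just before the GDS-12R and MLQ could colour the answers. The plan does not say which comes first.

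**Working it through.** **Order of events in NH-B, from the protocol**

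1. Screening and consent: family sheet available to those who want it (section 10.0).
2. Wait until recruitment is complete (sections 8.0 and 10.0).
3. First visit: overview, consent review, pre-test measures (section 10.0).
4. Four weeks of care as usual, with weekly postcards and a reminder call (section 10.0).
5. Post-test 1: measures, repeated overview, consent review, in no stated order (sections 10.0 and 21.0).
6. LSB visits.

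The sheet comes at step 1 and LSB at step 6. No statement postpones gathering to step 6, and none has it recorded if it starts sooner. At step 3 the protocol describes the overview and consent review ahead of the measures, so repeating that order at step 5 would be natural.

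**Can the dilution be sized?** Not from the documents. They give neither the share of residents who would take up the sheet nor the effect of gathering alone. What follows is purely illustrative.

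The plan's own figure comes first. Section 5.0 describes "A power analyses for a MANOVA, with 2 groups and 2 dependent variables", with alpha .05, effect size .94, N = 20 and power 95%. For the global test:

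- df1 = 2 and df2 = N − 3 = 17
- noncentrality λ = f² × N

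Entering .94 as f² gives λ = 0.94 × 20 = 18.8 and power 95.2%, which reproduces the plan. Section 5.0 labels .94 as d. Read as a standardised difference on each of two uncorrelated outcomes, f² = 2 × (0.94/2)² = 0.4418 and power is 68.0%. That discrepancy is a separate matter, so both readings are shown.

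Suppose NH-B obtains an average share c of the LSB effect, on both outcomes, before post-test 1. The contrast is multiplied by (1 − c) and f² by (1 − c)²:

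| Assumed c | f², reading that reproduces the plan | Power | f², reading as d on both outcomes | Power |
|---|---|---|---|---|
| 0 | 0.940 | 95.2% | 0.442 | 68.0% |
| 0.10 | 0.94 × 0.81 = 0.761 | 90.0% | 0.358 | 58.3% |
| 0.20 | 0.94 × 0.64 = 0.602 | 81.7% | 0.283 | 48.1% |
| 0.30 | 0.94 × 0.49 = 0.461 | 69.9% | 0.216 | 38.1% |

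Since c is an average over the home, it is the fraction of residents who gather times the share of the effect each obtains. With 10 residents, c = 0.10 would need, for example, 2 of them each to obtain half the full effect (0.2 × 0.5). A value of 0.30 would need 6 of 10 to do so (0.6 × 0.5). The documents support no particular value above 0.

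**The case against.** The other side has a good deal of force.

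- **The sheet is optional.** It gives information to residents who want it; it is neither a request sent to every family nor collection of material. It is also an attachment that is not in the text, so it may carry its own timing instructions. This stands: contamination is possible, not established.
- **LSB itself is not delivered early.** It is three guided one-hour visits plus the assembly of a book, and nothing gives NH-B these before post-test 1. A reader might infer that the care-as-usual phase already contains LSB and that the contrast is distorted. The documents do not support that; they show only that one component is not held back.
- **Most early contact is shared.** Life-review examples are shown as "questions as part of the informed consent process" (section 20.0), and all 24 participants meet their research assistant at the first visit. A reader might count these as NH-B exposures. They are common to both homes and fall at or before the pre-test visit, so they do not separate the homes. Only activity that continues in NH-B during the wait can do so.
- **The overview is mostly logistics.** It repeats what residents heard at the first visit and comes at the end of the wait. It matters only if it precedes the measures, and any effect could go either way.
- **The same-week sentence may be loose wording.** Read literally it would remove the comparator phase. The sentence before it concerns scheduling the first visit, and the stagger is explicit elsewhere in section 10.0, so it is no evidence that NH-B has LSB early. The conflict in the text remains.

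What survives is the gap itself. Pre-test adjustment does not answer gathering that takes place after the pre-test in NH-B.

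**Conclusion.** The point holds as a cheap improvement to the plan. It does not show that the trial's comparison is invalid. The stated timing lets photo and memorabilia gathering fall within NH-B's care-as-usual phase, or before the pre-test in either home, and no safeguard or record is provided. If that happened and had any benefit, it would tend to shrink the post-test 1 contrast. The size cannot be calculated, and the figures above show only how power would respond to assumed values.

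The conclusion assumes that some NH-B residents take up the offer before post-test 1, that gathering alone has some effect, and that the unseen sheet does not itself defer gathering. The unset order of overview, consent review and measures is a smaller gap of unknown direction. The sentence that starts all LSB visits in the same week is a definite conflict with the staggered start, but mainly one of wording.

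**What to change.** Amend section 10.0 as follows.

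1. Time the family sheet to each home's LSB. In NH-A, give it at the end of the first visit, after the pre-test measures. In NH-B, give it at the end of the post-test 1 visit, after the measures. Do not restrict residents' ordinary contact with family. Record, by home, any gathering begun before LSB, asking about it after the measures.
2. At post-test 1 in both homes, administer the GDS-12R and MLQ before any overview or consent review. Make section 21.0 consistent with this.
3. Reconcile the sentence on LSB visits beginning in the same week with the staggered start in Study Design and in the NH-B schedule.

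The cost is protocol wording and one brief item to record, with no added visits, staff or outcome measures. The downside is a shorter lead time for families to find material before the three LSB visits, though it would then be similar in the two homes.

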**6.0      Recruitment Methods**

Upon IRB approval, the two NHs will be contacted by telephone and email to provide follow-up information about this research study, its objectives and their role in recruitment. (*Please see attached*). A meeting will be scheduled with the request to meet as many of the NH's management team as possible. For these face-to-face meetings informative flyers with background information and simplified research procedures will be provided. (*Please see attached*). In addition, every effort will be made to recognize the NH's contribution to the study including: a plaque for participation, a presentation of the results of the study, and an LSB toolkit donated for continued use with other residents. This toolkit will include: portable scanner, scrapbook albums, audio recorder, USB flash drives and pad and pens.

NH administrators will be asked for the name of a staff member who might serve as an on-site point of contact. This site coordinator would be the research team's point of contact for scheduling, data collection and other communication between the research team, participants and the facility. NH staff have many demands for their time, so this site coordinator will be offered a stipend of \$300.00; \$150.00 halfway through the data collection (or at post-test 1) and \$150.00 when the data collection is complete (or at post-test 2).

Non-probability voluntary sampling method will be used to recruit participants from these two NHs. The NH administration, together with the PI, will identify potential participants. If there is an active resident council at the NH, this group may be contacted in order to introduce the study and recruit potential participants. Every NH, certified by Medicare and Medicaid, must provide a space for councils to meet. Resident councils are a group of residents that meet on a regular basis to discuss concerns, provide suggestions and plan activities for the NH [34].

Additional information meetings will be arranged, as needed, with the assistance of the NH administration, to describe the study and to answer residents', staff, and any family members' questions. (*Please see attached information flyer*).

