## **10.0 Procedures Involved**

### *Study Design:*

A quasi-experimental switching replication design will be employed to examine the effects of LSB on depressive symptoms and MIL for residents of NHs who are mentally alert by comparing post-test scores, while controlling for pretest scores. Two comparable NHs will be randomly allocated to NH-A or NH-B, indicating which home will begin LSB first, whereas the other home will receive care as usual. Participants in the same NH will receive the same intervention. A summary of the design is as follows:

Nursing Home A (NH-A):	Pretest	LSB	Post-test	CAU	Post-test
Nursing Home B (NH-B):	Pretest	CAU	Post-test	LSB	Post-test (CAU = care as usual)

Both NHs will eventually receive the LSB intervention, which will provide another opportunity to test outcome measures and allow for two independent implementations of the LSB intervention. This is one of the more ethically feasible designs because all participants will eventually receive the intervention. Furthermore, the additional post-test for NH-A, after one month, will examine the lasting effects of the LSB intervention.

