Potential participants who do not meet the inclusion criteria will be informed that for this study they are not eligible. No identifying information will be collected. They will also be informed that a presentation of the study results will be presented at their NH at a later date, to which they are invited to come and hear the results.

Two RAs will be randomly assigned six participants from each of the two NHs. Each will conduct individual LSB sessions with these six participants per NH, or twelve from both homes.

For the first visit, all 24 participants will be individually visited by the PI and the RA assigned to those participants. Each RA will only visit those participants whom they will be providing the intervention. An overview of the study will be reviewed, as well as information regarding the number of visits and length of time for each visit (1 hour). This first visit will also be a time for the participants to get acquainted with their RA. Participants will review the consent form signed in the initial screening interview which will include the purpose, procedures, risks and costs of participating in the LSB, as well as the protection of confidentiality from the RA and the PI. They will also be reminded of their rights as participants. The participants, at the beginning of each visit, will be told that they can stop and rest at any time or may reschedule the session if they become too fatigued to continue.

The PI will administer all measures face-to-face on a tablet, which will include the MLQ and the GDS-12R. In addition, the PI will collect orally from the participants their demographic information and their functional status (Katz ADL) onto a tablet.

**FULL PROTOCOL TITLE:** The Effectiveness of Life Story Book on Depression and Meaning in Life for Mentally Alert Residents of Nursing Homes

At this first visit, a written reminder card will be given to each participant with the date, time and contact information of their RA and their next scheduled visit. (*Please see attached*). Scheduled visits will be done at the most convenient time for the participant with careful consideration of scheduled activities, i.e. meals, naps, medicine. All future visits will be scheduled at this time, with the understanding that the RA will be flexible to the needs of the participant.

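### Visits that differ by home are booked at the pre-test visit, so the PI takes essentially every pre-test knowing the home's sequence; drawing the homes after the last pre-test would avoid this

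*Combined protocol and SAP*

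**What the plan says.** Under Study Design in Section 10.0, "Two comparable NHs will be randomly allocated to NH-A or NH-B". The protocol does not give the date of the draw, who makes it, or whether anyone is masked to it.

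The procedures in the same section then put three things into one visit:

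- **Who attends.** "For the first visit, all 24 participants will be individually visited by the PI and the RA assigned to those participants".
- **Measurement.** "The PI will administer all measures face-to-face on a tablet, which will include the MLQ and the GDS-12R".
- **Booking.** "All future visits will be scheduled at this time", and each resident leaves with a reminder card for the next visit.

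The bookings are not the same in the two homes. By the design summary, NH-A moves from pre-test to LSB. For the other home, "NH-B participants will be scheduled for post-tests in 4 weeks", and "A written postcard will be given to each participant with the date, time and contact information of their RA for their scheduled post-test".

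Section 25.0 uses the pre-test scores as covariates in the one-way MANCOVA that compares LSB with control on the GDS-12R and MLQ.

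**The concern.** Bookings that depend on the home's sequence cannot be made before the sequence is known. If they are made at the pre-test visit, the person who reads out the items and records the answers already knows which home starts LSB. The pre-test is the one assessment that could be kept free of this knowledge without another assessor.

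At stake is the adjustment. MANCOVA treats a between-home difference in recorded pre-tests as a real difference between residents and corrects the post-test comparison for it. If part of that difference comes from how the interviews were conducted, the correction itself creates a treatment difference. With 10 to 12 residents per home and one home per sequence, nothing in the data could separate the two sources.

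**Working it through.** **Step 1. Is the sequence known at the pre-test?** The draw date is not stated, so it has to be inferred from Section 10.0.

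- All later visits are fixed at the first visit.
- The content of those visits depends on whether the home is NH-A or NH-B.
- The booking therefore needs the result of the draw.

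**Step 2. How many pre-tests are affected?** Suppose, most favourably, that the measures come before the booking within each visit and that the draw is revealed only when the first resident is booked. There are two homes and one draw, so that single booking reveals the sequence of both. At most 1 pre-test is taken without knowledge, leaving 24 − 1 = 23 of 24 (or 20 − 1 = 19 of 20 at minimum recruitment). If the draw comes before the first visit, it is 24 of 24.

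**Step 3. How does a shift reach the result?** For one outcome,

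adjusted difference = (post A − post B) − slope × (pre A − pre B).

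A shift in one home's recorded pre-tests moves the adjusted difference by slope × shift, with opposite sign. Neither quantity is in the documents. Illustrative values, in SD units:

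| Assumed slope | Shift 0.2 | Shift 0.3 |
|---|---|---|
| 0.5 | 0.5 × 0.2 = 0.10 | 0.5 × 0.3 = 0.15 |
| 0.7 | 0.7 × 0.2 = 0.14 | 0.7 × 0.3 = 0.21 |

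**Step 4. Check by simulation.** The set-up was a single-outcome ANCOVA with 10 residents per home, no true effect, no home effect, a two-sided 5% test and 10,000 runs per setting. A pre-test shift of 0.25 SD gave:

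| Pre/post correlation | Slope × shift | Simulated move | Type I error |
|---|---|---|---|
| 0.5 | 0.125 | 0.13 | 6% |
| 0.7 | 0.175 | 0.17 | 8% |
| 0.8 | 0.200 | 0.20 | 10% |

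With no shift, type I error was about 5%.

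**Step 5. Can this be scaled to the planned effect?** The plan gives no figure on this point itself. Section 5.0 states 95% power at N = 20 with an effect of .94, labelled d. For a MANOVA with 2 groups and 2 outcomes, df = 2 and 17.

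- With .94 entered as f², λ = 20 × 0.94 = 18.8 and power is 0.952, which matches.
- With .94 as a multivariate standardised distance, f² = 0.94²/4 = 0.2209, λ = 4.418 and power is 0.388, which does not match.

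So .94 may not be on the SD scale, and the figures above should not be expressed as a share of it.

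**The case against.** **The timing is an inference.** The statement about NH-B's post-test booking does not itself name the first visit; that comes from reading it with the sentence on future visits. The attached timeline is not available here, and the RA might do the booking out of the PI's hearing. This is fair, and it is why the point is put as what follows from the text as written. But the PI and RA make that visit together, and no masking step is described.

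**The measures are fixed-format self-report.** The GDS-12R is yes/no and the MLQ is a 7-point scale, so there is no clinical rating for expectation to move. Influence through oral delivery remains possible, but its size and direction are unknown. This stands, and it is why the SD figures are illustrations only.

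**The same PI takes the post-tests knowing the sequence**, up to 2 × 24 = 48 interviews, with or without the change. This also stands. With slope 0.7, a post-test shift of 0.25 SD alone gives about 11% type I error. An opposite pre-test shift of the same size raises this to about 22%. If both shifts ran the same way they would partly cancel (0.25 − 0.7 × 0.25 = 0.075 SD), so the net gain depends on direction. That is no reason to rely on one bias offsetting another.

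**A stronger reading.** Since "The NH administration, together with the PI, will identify potential participants", a reader might infer that selection of residents is biased by knowledge of the allocation. The documents do not support that. They do not place the draw before recruitment, first visits are scheduled only once recruitment levels are met, the consent explanation is not split by home, and every resident eventually receives LSB. What can be said is narrower: the text does not guarantee that recruitment closes before the draw.

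**Conclusion.** The point holds for the pre-tests. As Section 10.0 is written, at least 23 of 24 pre-test interviews are taken by a PI who knows the home's sequence, and the resulting scores are the covariates of the main analysis. This rests on reading the booking sentence and the home-specific schedules together, and on no masking step existing in material not available here.

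The consequence is a possible bias of slope × shift. The 0.10 to 0.21 SD range depends wholly on the assumed shift of 0.2 to 0.3 SD and slope of 0.5 to 0.7. It is neither an estimate nor a fraction of the planned .94. The protocol claims no blinding and calls itself quasi-experimental, so this is not a contradiction in the plan. It is an avoidable weakness with an inexpensive remedy, though a smaller one than the unmasked post-tests and the confounding of home with treatment.

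**What to change.** In Section 10.0:

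- State that the draw of which home is NH-A is made only after every participant in both homes has consented and completed the pre-test. Say who makes the draw.
- Move the home-specific bookings, reminder cards and the NH-B postcard from the first visit to after the draw. The existing channels suffice: the paid site coordinator (Section 6.0), residents' preferred means of notification, and RA calls or postcards.
- Keep the same-week start of LSB visits, and say from which date NH-B's four weeks run, so that the delay does not make the pre-to-post interval differ between homes.

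Pre-tests taken with the sequence known then fall from at least 23 of 24 to 0 of 24, and recruitment is certain to close before allocation is known. Sample size, alpha and nominal power do not change.

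The cost is more than wording. Each resident needs one further scheduling contact, which must still fit around daily routines and any hearing or vision difficulty. No booking can be made until the last first visit is done; at 60 to 90 minutes each (Section 8.0), 24 visits take 24 to 36 hours of PI time, already in the plan. No extra staff or assessments are needed.

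The report should still state that the post-tests were unmasked and that each sequence had one home.
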